9.2 The Number of Participants

The number of participants is limited to 30 for practical reasons, based on the expected rate that participants can be recruited.

The following rationale was applied to determine this as an acceptable number of samples:

⁴ <https://www.hra.nhs.uk/approvals-amendments/managing-your-approval/safety-reporting/>, accessed 16/Aug/2021

- This is a Class I (MDD), low-risk device, and risk management according to ISO 14971 has been used to predict a favourable overall risk/benefit ratio.
- Bench testing has been carried out to verify that the design meets the specifications.
- Limited validation of the headgear has been carried out to partially show that the device is fit for purpose. This included testing on humans but without the endoscope inserted into them. The results demonstrated to a large extent that the design is safe and effective.

9.3 The Level of Statistical Significance

A conservative level of significance of $p=0.01$ will be used to control the false discovery rate, due to the expected small limiting sample size (Harrell, 2015).

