4.4 Rationale for Current Study

A headgear is necessary to carry out CLE tests for the investigations of EILO, as the endoscope must be kept stable for both image quality and patient safety. There is no commercial option existing on the market at present, and other centres have manufactured their headgear in-house (Liverpool Heart and Chest Hospital (LHCH), Royal Brompton Hospital).

Without a specialised headgear it is not possible to carry out CLE tests at LUHFT, and patients are sent for investigations at LHCH. This study is an essential step in improving the care that can be offered by LUHFT for sufferers of EILO. Evaluating the in-house design of headgear is necessary to support its safe and effective clinical use in accordance with the Medical Device Directive (MDD) 93/42 and in the spirit of the European Medical Device Regulations (MDR) 2017/745. By producing an in-house manufactured headgear, it will enable LUHFT to provide an additional service for patients, avoiding the inconvenience to them of having to travel further afield.

Therefore, the hypothesis for this study is that the HALOS headgear is sufficiently effective for clinical use, and that the risks are understood adequately for an accurate benefit/risk ratio evaluation.

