9. STATISTICS

9.1 Description of Statistical Methods

A single proportion test will be applied to the primary outcome measure (see Section 6.2.1), using a reference proportion of 49 in 50. This is derived from a clinical estimate of the threshold for acceptable performance of the headgear being where the resulting endoscopy image is not sufficiently clear and stable in no more than 1 in 50 cases.

The secondary outcome measures (see Section 6.2.2) will be used as follows:

- The device usability and tolerability ratings will be used to support the risk/benefit ratio assessment of the device.
- Device usability and tolerability subjective feedback will be used to inform and prioritise how residual risks associated with usability and tolerability can be reduced.

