12.3 Approvals

The protocol, informed consent form, participant information sheet and any proposed advertising material will be submitted to an appropriate REC, Health Research Authority and host institution(s) for written approval. Local capacity and capability approval will be sought from each participating NHS organisation.

A letter of no objection from the MHRA is not required as this is not a clinical investigation of a device intended to be UKCA/CE-marked, or commercialised.

The Investigator will submit and, where necessary, obtain approval from the above parties for all substantial amendments to the original approved documents.

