16. PUBLICATION POLICY

An internal report will be produced detailing the findings from the study in the form of a clinical evaluation in line with MEDDEV 2.7/1 Clinical Evaluation: A Guide for Manufacturers. The study will also be used to update the Risk Log for the device.

Although the main reason for this Study is it to enable LUHFT to provide an additional service for patients, publication in a peer reviewed scientific journal or as a report on our website will be considered to disseminate the findings of this study to interested parties.

Authors will be defined as those who have made:

- Substantial contributions to the conception or design of the work; or the acquisition, analysis, or interpretation of data for the work; **AND**
- Drafting the work or revising it critically for important intellectual content; **AND**
- Final approval of the version to be published; **AND**
- Agreement to be accountable for all aspects of the work in ensuring that questions related to the accuracy or integrity of any part of the work are appropriately investigated and resolved.

Contributors who have contributed materially to the paper but whose contributions do not justify authorship will be described clearly in acknowledgements.

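### The primary test against 49 in 50 has no stated direction, version or pass rule, and 30 participants cannot show that the headgear meets the 1-in-50 limit

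*Combined protocol and SAP*

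**What the plan says.** Section 9.1: "A single proportion test will be applied to the primary outcome measure", with a reference of 49 in 50. That reference comes from a clinical estimate of the "threshold for acceptable performance of the headgear", namely at most one unusable image in 50 tests. The section states no null or alternative hypothesis, no sidedness, no choice between an exact and a normal-approximation test, and no meaning for a significant or a non-significant result. No test is planned for the secondary ratings and feedback, which inform the risk/benefit assessment and the reduction of residual risks.

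Section 9.2: "The number of participants is limited to 30 for practical reasons". It gives no power, alternative proportion or critical count. It supports the number by pointing to the low-risk class, bench testing and limited earlier validation.

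Section 9.3 sets the level at 0.01, calls it conservative, says that it "will be used to control the false discovery rate, due to the expected small limiting sample size", and cites a textbook.

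Section 4.4 puts the study hypothesis in words only: "the hypothesis for this study is that the HALOS headgear is sufficiently effective for clinical use", and adds that the risks should be adequately understood. Section 16 gives the destination of the results: "An internal report will be produced detailing the findings from the study in the form of a clinical evaluation".

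**The concern.** A significance level protects against a particular wrong conclusion, and the plan does not say which one. Two readings are open.

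- **Reading 1, significance means success.** The test tries to show that the true proportion exceeds 0.98, as the Section 4.4 hypothesis may suggest.
- **Reading 2, significance means shortfall.** The device is accepted unless it is significantly below 0.98. The documents do not state this; it is an inference from the reference being a threshold for acceptability.

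Under Reading 1 it matters whether any result with 30 participants can succeed. Under Reading 2 a smaller level makes it harder to flag a poor device, so calling 0.01 conservative points the wrong way for the decision to accept. Under either reading the version of the test can change the result, and if it is not fixed beforehand it can be chosen after the data are seen.

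At stake is what the clinical evaluation may claim. A non-significant result at a level described as conservative could be taken as evidence that the 1-in-50 limit is met.

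**Working it through.** **Inputs.** n = 30 (Section 9.2; withdrawn participants are replaced under Section 6.5, so 30 evaluable tests are assumed). Reference p0 = 49/50 = 0.98 (Section 9.1). Level 0.01 (Section 9.3). The 0.05 level and the true failure rates below are illustrative assumptions, since the plan gives no alternative. The plan has no derived figure to reproduce: 30 is a practical limit and 0.01 is simply chosen.

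**Step 1. Reading 1, best possible result (30/30), one-sided.**
- Exact: 0.98^30 = 0.545.
- The null standard deviation of the count is √(30 × 0.98 × 0.02) = √0.588 = 0.7668, and the expected count is 29.4.
- Uncorrected z = (30 − 29.4)/0.7668 = 0.782, p = 0.217.
- Continuity-corrected z = (30 − 0.5 − 29.4)/0.7668 = 0.130, p = 0.448.

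No version reaches 0.05, let alone 0.01. With no failures at all, an exact test needs ln(0.05)/ln(0.98) = 148.3, so 149 participants, at 0.05. At 0.01 it needs ln(0.01)/ln(0.98) = 227.9, so 228. The exact (Clopper-Pearson) two-sided lower limit at 30/30 is 0.025^(1/30) = 88.4% at 95% and 0.005^(1/30) = 83.8% at 99%, both well below 98%.

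**Step 2. Reading 2, one-sided exact test for shortfall.** At a true failure rate of 2%, P(3 or more failures in 30) = 0.0217 and P(4 or more) = 0.0029. The flag is therefore 3 or more failures at 0.05 and 4 or more at 0.01.

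| True failure rate | Flagged at 3 or more (level 0.05) | Flagged at 4 or more (level 0.01) |
|---|---|---|
| 2% (at the limit) | 2.2% | 0.3% |
| 5% | 18.8% | 6.1% |
| 10% | 58.9% | 35.3% |
| 15% | 84.9% | 67.8% |
| 20% | 95.6% | 87.7% |
| 30% | 99.8% | 99.1% |

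At a 10% failure rate, five times the limit, the 0.01 rule misses the device 100 − 35.3 = 64.7% of the time. An 80% chance of flagging needs a true failure rate of 13.7% (3 or more) or 17.6% (4 or more).

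**Step 3. Version of the test, at 27/30 (observed failure rate 10%).**
- Exact: p = 0.0217.
- Uncorrected z = (27 − 29.4)/0.7668 = −3.130: p = 0.0009 one-sided, 0.0017 two-sided.
- Corrected z = (27.5 − 29.4)/0.7668 = −2.478: p = 0.0066 one-sided, 0.0132 two-sided.

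At 0.01 the exact test and the two-sided corrected z do not flag; the other three do. The normal approximation is unsuitable here because n·p0·(1 − p0) is only 0.588. The uncorrected z flags at 3 failures but not at 2 (28/30 gives one-sided p = 0.0339), so its true size is 0.0217, more than twice the nominal 0.01.

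**Step 4. The Section 9.3 rationale.** Only one test is planned, so there is no family of tests over which a false discovery rate could be controlled. The other sense, the chance that a single significant result is false, needs a prior and a power to be quantified, and neither is given.

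**The case against.** Several points on the other side are sound.

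**The false-discovery rationale has some logic.** The chance that a significant result is false rises with the ratio of size to power, so with low power a stricter level is a coherent qualitative choice. Under Reading 2 at an assumed 10% failure rate, the ratio is 0.0217/0.589 = 0.037 with the 0.05 rule and 0.0029/0.353 = 0.0082 with the 0.01 rule, about 4.5 times lower. This stands. A reader might infer that nothing supports the level, but Section 9.3 does give a reason and a citation, whose content cannot be judged from the documents. What remains is that the rate is neither defined nor quantified, and that under Reading 2 the finding being protected is one against the device.

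**The level is not the main cause.** Reading 1 fails at 0.05 as well. The defect is 30 participants against a reference of 0.98 with no stated rule, which belongs to Sections 9.1 and 9.2. This stands.

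**Protection is not absent.** A reader might infer that the level gives no usable protection. The figures do not support that: once an exact shortfall test is fixed, size is capped at 0.3%, and a device failing 20% or 30% of the time is flagged 88% or 99% of the time. The weakness is against moderate shortfall.

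**The p-value is not the adoption rule.** A reader might infer that this test decides clinical use. No section says so. Usability and tolerability ratings also feed the risk/benefit assessment, Section 4.4 has a second limb on understanding the risks, the synopsis calls this a device development study, and Section 9.2 is open that 30 is a practical limit. This limits the consequence but does not give the planned test a meaning.

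**Conclusion.** The point holds, as something that should be corrected. The planned test cannot support the effectiveness hypothesis in the device's favour: the best possible outcome has an exact p of 0.545. That depends only on n = 30 and the reference of 0.98. If the test is meant to find shortfall, which is an inference, an exact test at 0.01 flags at 4 or more failures and misses a device with an assumed 10% failure rate about 65% of the time. In that direction the smaller level favours the device. With the version unstated, 27/30 falls on either side of 0.01.

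The Section 9.3 wording is a lesser matter: 0.01 is a per-test type I error level, and false-discovery-rate control is asserted without being defined.

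**What to change.** **Section 9.1.** Report the primary proportion with an exact (Clopper-Pearson) interval. State that 30 participants cannot demonstrate 98% and that a non-significant result does not show it.

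If a check against 0.98 is kept, give H0 and H1, name a one-sided exact test for shortfall, and state its failure count and its operating characteristics at the level that the sponsor chooses. The table above supplies them: 4 or more failures at 0.01, or 3 or more at 0.05. The choice is the sponsor's trade-off between false flags and missed shortfall.

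Match the interval to the retained test. At 27/30 the 95% interval (73.5% to 97.9%) excludes 98% while the exact test at 0.01 does not flag; the 99% interval (68.0% to 98.8%) agrees with that test. At 26/30 the test flags and the 99% upper limit, 97.7%, also excludes 98%.

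**Section 9.3.** Replace the conservative and false-discovery-rate wording with a statement of the type I error being controlled.

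**Cost.** Wording only, with no extra participants or data. The changes may fall under Section 12.3, by which the investigator must, where needed, "obtain approval from the above parties for all substantial amendments to the original approved documents". The downside is a less favourable statement of what the trial can conclude. The fix also adds no power: at an assumed 5% failure rate the device is still missed 81.2% of the time with the 3-failure rule and 93.9% with the 4-failure rule.

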9.4 Criteria for the Termination of the Trial

The trial will be terminated in the event of any device-related SAE, SADE or USADE.

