8.1.2 Adverse Event (AE)

Any untoward medical occurrence, unintended disease or injury or any untoward clinical signs (including an abnormal laboratory finding) in subjects, users or other persons, whether or not related to the investigational medical device and whether anticipated or unanticipated.

This includes events related to the investigational device or the comparator and events related to the procedures involved (any procedure in the study protocol). For users or other persons, i.e. where the medical occurrence, unintended disease or injury is not in the subject, this definition is restricted to events related to the use of investigational medical devices or comparators.

No potential AEs are identified.

The categories of adverse events are shown in Table 1.

³ Source: BS EN ISO 14155:2020 Clinical Investigation of Medical Devices for Human Subjects – Good Clinical Practice.

Table 1: Categories of adverse events (taken from BS EN ISO 14155:2020 Table F.1)

Adverse events	Non-device-related	Device- or investigational procedure-related	
Non-serious	Adverse event (AE) ^a (3.2)	Adverse device effect (ADE) ^c (3.1)	
Serious	Serious adverse event (SAE) ^b (3.45)	Serious adverse device effect (SADE) (3.44)	
		Anticipated	Unanticipated
		Anticipated serious adverse device effect (ASADE) ^c (3.1, Note 1 to entry)	Unanticipated serious adverse device effect (USADE) (3.51)

^a Includes all categories.
^b Includes all categories that are serious.
^c Includes all categories that are related to the device or the investigational procedure.

8.1.3 Serious Adverse Event (SAE):

SAE is an adverse event that led to any of the following:

- death
- foetal distress, foetal death or congenital abnormality or birth defect including physical or mental impairment.
- serious deterioration in the health of the subject, users or other persons as defined by one or more of the following:
 - a life-threatening illness or injury
 - a permanent impairment of a body structure or a body function including chronic diseases
 - in-patient or prolonged hospitalisation
 - medical or surgical intervention to prevent life-threatening illness or injury, or permanent impairment to a body structure or a body function

Planned hospitalisation for a pre-existing condition, or a procedure required by the Study Protocol, without serious deterioration in health, is not considered a serious adverse event.

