15. END OF STUDY DEFINITION

The study will formally end when the data collection has been completed from the last participant and data analysis is complete.

The study will be ended prematurely by the CI in the following cases:

- A SADE or USADE occurs;
- A DD is identified that might have led to a SADE if suitable action had not been taken, intervention had not been made or if circumstances had been less fortunate;
- Emergent information about the device risk causes the risk/benefit evaluation to become unfavourable.

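### Do a wider table heading for serious adverse device effects and a shorter list in section 9.4 leave the stopping rule unsettled?

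*Combined protocol and SAP*

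**What the plan says.** Two sections say when the study ends early. Section 9.4 has one sentence: "The trial will be terminated in the event of any device-related SAE, SADE or USADE". Section 15 opens with "The study will be ended prematurely by the CI in the following cases" and lists three:

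- "A SADE or USADE occurs"
- "A DD is identified that might have led to a SADE if suitable action had not been taken", a condition that continues with two further near-miss alternatives
- "Emergent information about the device risk causes the risk/benefit evaluation to become unfavourable"

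Both depend on what counts as a SADE. Section 8.1.4 defines an adverse device effect (ADE) as an event related to use of the device, with causality judged against the device. Section 8.1.5 defines a SADE as an ADE with a serious outcome, and 8.1.6 defines an unanticipated SADE (USADE) as a kind of SADE. The investigational procedure appears in none of these three definitions.

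Table 1, in section 8.1.2, groups the same terms under "Device- or investigational procedure-related". Its footnote c, marked on the ADE and anticipated-SADE cells, reads "Includes all categories that are related to the device or the investigational procedure". The table is captioned as taken from a published standard. The protocol does not say what an investigational procedure is.

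**The concern.** A term that ends a study should have one meaning. On the table's scope, a serious event caused by the endoscope or the exercise, with no contribution from the headgear, could be a SADE, and section 15 would end the study. On the scope of 8.1.4 and 8.1.5 it is not a SADE. The study would continue, and under section 6.5 the participant could be withdrawn and replaced. Section 15 puts no qualifier on its SADE case, so it does not settle the matter by itself.

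The second worry is that section 9.4, whose title promises the termination criteria, omits the near-miss device deficiency and the unfavourable shift in risk and benefit, and does not point to section 15. Someone using 9.4 alone would miss both.

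At stake is whether the study stops at some participant before the planned 30 or carries on, with the decision left to argument after the event.

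**Working it through.** The plan states no figure on this point, so there is none to reproduce. The check sets the sections side by side and asks, for each kind of event, whether the readings give different decisions.

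| Event | SADE under Table 1? | SADE under 8.1.4–8.1.5? | Does the study end? |
|---|---|---|---|
| Serious, headgear suspected as a cause | Yes | Yes | Yes, under both 9.4 and 15 |
| Serious, endoscopy or exercise only, test regarded as routine care | No | No | No device or procedure trigger on either scope |
| Serious, endoscopy or exercise only, test regarded as an investigational procedure | Yes | No | Section 15 depends on the scope used |
| Serious, unrelated to device and test | No | No | No device or procedure trigger on either scope |
| Near-miss device deficiency | Not applicable | Not applicable | Yes, under 15; 9.4 is silent |
| Risk/benefit turns unfavourable | Not applicable | Not applicable | Yes, under 15; 9.4 is silent |

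**Scope.** Only the third row splits the readings, and it requires two things.

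1. Neither the reporting clinician nor the sponsor suspects the headgear. Under 8.1.4 a reasonable suspicion by either one makes the event an ADE, so cases of mixed cause fall in the first row.
2. The test counts as an investigational procedure. Section 6.3.1 recruits patients already selected for the test, 6.3.2 requires a clinical need for it, and 6.4.4 says it follows standard practice. Those statements describe routine care with a new accessory. On the other side, 6.1 describes the trial as participants having the test with the headgear, 4.4 says the site cannot run the test without such headgear, and 6.4.4 includes endoscope insertion and removal in its sequence of headgear-related steps. These show that the test and the device are used together, but they do not classify the test as investigational.

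The sources can then be compared. Sections 8.1.4, 8.1.5 and 8.1.6 form one chain, all on device scope. Section 9.4 uses the words device-related. The second and third cases in section 15 concern a device deficiency and device risk. Table 1 with its footnote is the only source that adds the procedure, and its cells refer to numbered clauses of the standard. It sorts events into categories, while the headed subsections define the terms.

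**Lists.** Section 15 has 3 cases. Section 9.4 covers 1 (SADE or USADE), which leaves 3 − 1 = 2 uncovered. Section 9.4 does not say that its list is complete or that other grounds are excluded. Section 15 is mandatory and sits in the same document. Following both gives the section 15 list, and no event makes one section forbid what the other requires.

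**Replacement.** Section 6.5 concerns individual participants. Once the study has ended nobody is replaced, so 6.5 does not compete with 9.4 or 15.

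**Analysis.** None of the triggers looks at the primary outcome, so neither reading adds an interim test of the 49-in-50 reference proportion in 9.1. Stopping early would shorten the sample but would not alter the test.

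**The case for a change.** The strongest opposing case is that footnote 3 credits the section 8.1 definitions to the same standard from which Table 1 is taken, so the protocol gives no formal ground for ranking the definitions above the table. The qualifier in 9.4 can be read as attaching only to its first term, which would leave the scope of SADE open there too. Section 8.1.2 also counts "events related to the procedures involved (any procedure in the study protocol" when it defines adverse events, and problems caused by the endoscopy are foreseeable, since 6.3.3 has a list of exclusions for that procedure. A stopping rule should be clear before it is needed.

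Part of this stands. The table heading is literally wider than the definitions, and the undefined term is a real gap. The rest carries less weight. The procedure wording in 8.1.2 belongs to the general adverse-event definition, and being an adverse event does not make something an ADE under 8.1.4. If the qualifier in 9.4 attaches only to its first term, SADE still takes its meaning from 8.1.5. That the event is foreseeable does not make the test investigational. The omission from 9.4 is incompleteness and not contradiction, because both sections can be followed at once.

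**Conclusion.** No change to the plan is called for. This is a gap in drafting detail that the study team can fill sensibly from the protocol itself.

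Its size is one table heading with its footnote, set against three consistent definitions, and two of three stopping cases that appear in section 15 but are not repeated in 9.4. The readings give different decisions for a single kind of event: a serious one with no suspected headgear contribution, in a test that is regarded as an investigational procedure. The documents give no rate for such events, so no probability is claimed.

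Serious headgear-related events end the study on every reading. Section 8.3 requires serious events to be reported at once whatever their relation to the device, so a procedure-only event would reach the sponsor without delay. The endpoints, the primary test and the planned number of 30 are unaffected.

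The conclusion rests on reading 9.4 and 15 together and on taking the headed definitions in 8.1.4 to 8.1.6 as the working ones. If the sponsor did regard the laryngoscopy test as an investigational procedure, Table 1 and those definitions would have to be reconciled. Which rule is intended is for the sponsor, and no view is offered here. A cross-reference from 9.4 to 15 would be an editorial convenience.
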